5.8	Subject Withdrawal/Discontinuation Criteria	Added 'progressive' in the last sentence of a) Hypoglycemia (1).	Typographic error
7.1.1.11	Instruction for recording of patient's log and dispensing	Deleted 'the day after' to clarify the timing from when the patient's log is recorded.	Typographic error

1.0 TRIAL SUMMARY

Abbreviated Title	Omarigliptin Phase IV Study -Omarigliptin Add-on to Insulin in Japanese T2DM
Sponsor Product Identifiers	MK-3102 Omarigliptin
Trial Phase	Phase IV
Clinical Indication	Not Applicable
Trial Type	Interventional
Type of control	Placebo
Route of administration	Oral
Trial Blinding	Double-blind
Treatment Groups	Phase A; Omarigliptin 25 mg once weekly (q.w.) or placebo Phase B; Omarigliptin 25 mg once weekly (q.w.)
Number of trial subjects	Approximately 180 subjects will be enrolled.
Estimated duration of trial	The Sponsor estimates that the trial will require approximately 23 months from the time the first subject signs the informed consent until the last subject's last study-related phone call or visit.
Duration of Participation	Each subject will participate in the trial for up to 71 weeks from the time the subject signs the Informed Consent Form through the final contact. After a screening period of up to 2 weeks followed by a pre-treatment period of 2 or 10 weeks, each subject will be receiving assigned treatment for approximately 16 weeks (Phase A) and 36 weeks (Phase B). After the end of treatment each subject will be followed for 21 days.
Randomization Ratio	Subjects will be randomized in a 2:1 ratio to omarigliptin 25 mg once weekly (q.w.) or placebo and stratified by use of oral AHA at Visit 1/Screening

A list of abbreviations used in this document can be found in Section 12.3.

2.0 TRIAL DESIGN

2.1 Trial Design

This is a randomized, placebo-controlled, parallel-group, multi-site, double-blind trial and subsequent open-label, extension trial of MARIZEV®/omarigliptin (MK-3102) in Japanese subjects with type 2 diabetes mellitus (T2DM) who have inadequate glycemic control on insulin monotherapy in addition to diet and exercise therapy, to be conducted in conformance with Good Clinical Practices (GCP) and Good Post-marketing Study Practice.

Note: In the pre-treatment period, 'Group A' and 'Group B' are used to distinguish two groups of subjects: Subjects on oral anti-hyperglycemic agent (AHA) at Visit 1/Screening who require wash-out of the oral AHA from Visit 2/Week-10 (Group A) and subjects that are not on oral AHA at screening and therefore do not require washout (Group B). See the text provided below and Trial Diagram in 2.2 for the detail.

This trial consists of a screening period of up to 2 weeks, a pre-treatment period of 2 weeks or 10 weeks (which includes 2-week single-blind placebo run-in period), and a treatment period of 52 weeks. Subjects on insulin in combination with an oral AHA, (referred to as Group A) will have a pre-treatment wash-out period of 10 weeks (to wash-out the oral AHA),

and subjects on insulin in monotherapy with no other AHAs (referred to as Group B) will have a pre-treatment period (single-blind placebo run-in period) of 2 weeks. The treatment period is composed of a 16-week double-blind period (Phase A) and a 36-week open-label period (Phase B). Randomization will be stratified based on their use of an oral AHA at Visit 1/Screening (insulin + oral AHA or insulin monotherapy).

After the 2-week, single-blind, placebo run-in period, subjects will be randomized in a 2:1 ratio to receive either omarigliptin 25 mg once weekly (q.w.) or placebo, and they will take one tablet of trial medication (Omarigliptin 25 mg tablet or matching placebo tablet) once weekly (q.w.) orally for 16 weeks in a double-blind manner (Phase A). Subsequently in Phase B, all subjects will take one open-label tablet of omarigliptin 25 mg once weekly (q.w.) orally for 36 weeks.

Approximately 180 subjects will be randomized. The target randomized population includes Japanese patients ≥ 20 years of age with T2DM who have inadequate glycemic control on insulin monotherapy in addition to diet and exercise therapy, with hemoglobin A1c (HbA1c) $\geq 7.5\%$ and $\leq 10.0\%$ at Visit 3/Week -2.

[figure not shown]
Subjects on pre-mixed/fixed ratio combination (content percentage of rapid-acting or ultra rapid-acting insulin is lower than or equal to 30%), intermediate or long-acting insulin monotherapy are eligible to participate.

Consistent dosage and administration schedule of insulin will be used during the trial. In Phase A (double-blind period), the dosage must be kept at the dosage used at Visit 1/Screening, unless the subject meets hypoglycemia criteria for down-titration, or glycemic rescue criteria for up-titration of insulin. During Phase B (open-label period), the investigator can modify dose of insulin as clinically required for appropriate glycemic control, in addition to insulin adjustment based on the protocol-specified rescue/hypoglycemia criteria.

Specific procedures to be performed during the trial, as well as their prescribed times and associated visit windows, are outlined in the Trial Flow Chart - Section 6.0. Details of each procedure are provided in Section 7.0 – Trial Procedures.

2.2 Trial Diagram

The trial design is depicted in [Figure 1](#).

R = Randomization

*¹ During Phase B (open-label period), dosage adjustments of insulin will be allowed as clinically appropriate to manage the subject's glycemic control.

*² Subjects in Group B proceeds to Visit 3/Week -2 after Visit 1/Screening, skipping Visit 2/Week -10.

*³ If subjects in Group B performed the procedures of Visit 3/Week -2 within 2 weeks after Visit 1/Screening, HbA1c measurement is not needed at Visit 3/Week -2. The subjects may be deemed to meet the HbA1c criterion of Visit 3/Week -2 by HbA1c value of Visit 1/Screening.

*⁴ Visit 4/Day 1/Randomization is baseline.

Figure 1 Trial design

3.0 OBJECTIVE(S) & HYPOTHESIS(ES)

In Japanese patients with T2DM who have inadequate glycemic control on insulin monotherapy in addition to diet and exercise therapy:

3.1 Primary Objective(s) & Hypothesis(es)

1. **Objective:** To assess the efficacy of omarigliptin 25 mg q.w. compared to placebo based upon change from baseline in HbA1c at Week 16 [Phase A (double-blind period)].

Hypothesis: Omarigliptin 25 mg q.w. provides greater reduction in HbA1c compared with placebo as assessed by change from baseline to Week 16 [Phase A (double-blind period)].

2. **Objective:** To assess the safety and tolerability of omarigliptin 25 mg q.w. through 16 weeks [Phase A (double-blind period)].
3. **Objective:** To assess the safety and tolerability of omarigliptin 25 mg q.w. for up to 52 weeks [Phase A (double-blind period) and Phase B (open-label period)].

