8.6 Statistical Methods

Statistical testing and inference for efficacy and safety analyses are described in 8.6.1 and 8.6.2, respectively. Nominal p-values may be computed for other efficacy analyses as a measure of strength of association between the endpoint and the treatment effect rather than formal tests of hypotheses. All statistical tests will be conducted at $\alpha=0.05$, two-sided.

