baseline at Week 16 will be demonstrated using above cLDA model. The Kenward-Roger adjustment will be used with restricted (or residual) maximum likelihood (REML) to make proper statistical inference. An unstructured covariance matrix will be used to model the correlation among repeated measurements and hence avoids the potential bias that could result from the use of specific structured covariance models. If the unstructured covariance model fails to converge with the default Newton-Raphson algorithm, the Fisher scoring algorithm or other appropriate methods can be used to provide initial values of the covariance parameters. In the rare event that none of the above methods yield convergence, a structured covariance such as Toeplitz can be used to model the correlation among repeated measurements. In this case, the empirical option will be used because the sandwich variance estimator is asymptotically unbiased while the model-based variance estimator can grossly overestimate or underestimate the true variance. The cLDA model uses the maximum likelihood principle to estimate the parameters and account for missing data in an implicit fashion.

To avoid the confounding influence of rescue therapy on efficacy comparisons at Week 16, efficacy analyses in the FAS and PP populations will treat data as missing after the initiation of rescue therapy. Sensitivity analyses will be performed to assess the robustness of the results to the assumptions about missing data. The details will be described in sSAP.

Secondary efficacy endpoint of FPG at Week 16 will be analyzed using the above cLDA method described for HbA1c in the same fashion.

Analyses in the PP population for the primary and secondary efficacy endpoints at Week 16 will be performed using a repeated measures analysis of covariance (RM ANCOVA), in which the response vector consists of change from baseline at each of the post-baseline time points. The model will include the same terms for the cLDA model above, and baseline value as a covariate.

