8.9 Sample Size and Power Calculations

Efficacy analyses

A sample size of 180 subjects in a 2:1 ratio (i.e., 120 and 60 subjects for omarigliptin and placebo, respectively) will be equivalent to an effective sample size of 176 at Week 16 in the power calculation for the primary hypothesis test using the cLDA model. The effective sample size accounts for information loss due to missing data and the correlation among repeated measures, and is derived using the method proposed by Lu, et al. [17] under the assumptions of cumulative attrition rates and covariance matrix at Weeks 4, 8, 12, and 16 specified below. An effective sample size of 176 will provide 97% power to detect a treatment difference of 0.5% at Week 16 ($\alpha=0.05$, two-sided test) assuming the conditional standard deviation is 0.82%. In addition, it will provide 90% (80%) power to detect a treatment difference of 0.43% (0.37%). The half-width of the 95% CI is expected to be 0.26%. These calculations were based upon the following assumptions:

- Cumulative attrition rates, which include HbA1c data considered missing after rescue, at Weeks 4, 8, 12, and 16 are 0.0125, 0.0250, 0.0375, 0.0500, respectively
- A conditional correlation matrix at Weeks 4, 8, 12, and 16 is

$$\begin{bmatrix} 1.0 & 0.91 & 0.83 & 0.77 \\ 0.91 & 1.0 & 0.93 & 0.87 \\ 0.83 & 0.93 & 1.0 & 0.94 \\ 0.77 & 0.87 & 0.94 & 1.0 \end{bmatrix}$$

The cumulative attrition rates and correlation assumptions above are based on data from MK-0431 PN106.

Given the effective sample size above, the treatment difference of 25.0 mg/dL (21.6 mg/dL) can be detected with 90% (80%) power for the secondary efficacy endpoint, change from baseline in the fasting plasma glucose (FPG) at Week 16, assuming the conditional standard deviation is 48 mg/dL.

Safety analyses

The sample size is expected to provide 100 or more subjects exposed for one year (omarigliptin group only), assuming 15% discontinuation rate for 52 weeks.

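### The per-protocol RM ANCOVA fits one baseline slope to all visits, unlike the primary cLDA; if slopes differ by visit, the Week 16 per-protocol estimate loses some precision

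*Combined protocol and SAP*

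**What the plan says.** Section 3.1 states the primary hypothesis: omarigliptin "provides greater reduction in HbA1c compared with placebo as assessed by change from baseline to Week 16". It does not mention the PP analysis; the text at issue is in Section 8.6.1.

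There the primary analysis is a cLDA in the FAS. Baseline is part of the response vector and the covariance is unstructured. The model terms are treatment, prior AHA status, time, and interactions of these with time.

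For the PP population, the HbA1c and FPG analyses use an RM ANCOVA "in which the response vector consists of change from baseline at each of the post-baseline time points". On its terms the plan says: "The model will include the same terms for the cLDA model above, and baseline value as a covariate". None of the cLDA terms involves the baseline value, so this sentence adds baseline as a main effect only.

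Table 10 marks the PP analysis as a secondary approach. Section 8.5.1 commits to investigating substantial differences between FAS and PP conclusions.

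**The concern.** Read literally, treatment and prior AHA effects may change from visit to visit in the PP model, but the baseline slope may not. The primary cLDA has no such restriction, because an unstructured covariance that includes baseline implies a separate regression on baseline at each visit.

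HbA1c moves slowly, so the slope of change on baseline could well be flatter at Week 4 than at Week 16. The shared slope would then not be the Week 16 slope. Part of the baseline variation would stay in the Week 16 residual, and a chance imbalance between arms would be only partly removed. The FAS and PP analyses would also differ in how they adjust for baseline as well as in population, which makes a discrepancy between them a little harder to interpret.

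**Working it through.** **Inputs from Sections 8.6 and 8.9.** "A sample size of 180 subjects in a 2:1 ratio (i.e., 120 and 60 subjects for omarigliptin and placebo, respectively"); "All statistical tests will be conducted at $\alpha=0.05$, two-sided"; "An effective sample size of 176 will provide 97% power to detect a treatment difference of 0.5% at Week 16", "assuming the conditional standard deviation is 0.82"%; cumulative attrition "at Weeks 4, 8, 12, and 16 are 0.0125, 0.0250, 0.0375, 0.0500, respectively"; and the printed 4x4 conditional correlation matrix R.

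**Assumptions, not in the documents.** Baseline SD 0.7; slope of change on baseline at Week 16 between -0.22 and -0.40; the slopes at earlier visits; the conditional SDs at Weeks 4 to 12; unstructured covariance in the PP model; a PP set of 180 x 0.95 = 171 (114 and 57).

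**The plan's own figures reproduce.**
- Summing R-based information over the monotone dropout patterns (0.0125 lost before each visit, 0.95 complete) gives a Week 16 variance factor of 1.0227, so effective N = 180/1.0227 = 176.0.
- SE = 0.82 x sqrt(3/176 + 3/352) = 0.1311.
- Half-width = 1.96 x 0.1311 = 0.257 (stated 0.26).
- Power = Phi(0.5/0.1311 - 1.96) = 96.8% (stated 97%).

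**Effect of a shared slope.** Let b be the vector of true slopes of change on baseline at the four visits and S the conditional covariance. The fitted common slope is g = (1'S^-1 b)/(1'S^-1 1). The Week 16 variance ratio is 1 + (b16 - g)^2 x 0.7^2/0.82^2. Equal slopes give g = b16 and a ratio of 1.

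In the illustration below, the slope of change runs linearly from -0.05 at Week 4 to the Week 16 value, and the conditional SD runs linearly between the values shown.

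| SD, Week 4 to Week 16 | Weights on Weeks 4, 8, 12, 16 | b16 = -0.22: g, ratio | b16 = -0.40: g, ratio |
|---|---|---|---|
| 0.82 to 0.82 | 0.53, -0.07, 0.04, 0.50 | -0.135, 1.005 | -0.226, 1.022 |
| 0.60 to 0.82 | 1.09, -0.05, 0.04, -0.08 | -0.038, 1.024 | -0.026, 1.102 |
| 0.35 to 0.82 | 1.55, -0.34, -0.07, -0.14 | 0.001, 1.036 | 0.054, 1.150 |

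These and similar paths give about 0.5% to 2% with equal SDs and about 2.5% to 16% with growing SDs. They are illustrations, not bounds: a Week 4 slope of exactly zero takes the tops to 2.9% and about 20%.

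**What this means in 171 subjects.**
- No loss: SE = 0.82 x sqrt(1/57 + 1/114) = 0.1330, half-width 0.261, power 96.4%.
- Variance +2%: half-width 0.263, power 96.1%.
- Variance +16%: half-width 0.281, power 93.7%.

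**Imbalance.** The uncorrected shift is the imbalance times (b16 - g). For a baseline difference of 0.1 it is 0.009 to 0.017 in the equal-SD row, and 0.018 to 0.045 in the growing-SD rows.

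**Bias and type I error.** Simulation used 4000 runs per scenario, 114 vs 57, complete data, baseline SD 0.72 and equal SDs. Week 4 to Week 16 slopes of change ranged from equal to an extreme 0 to -0.70. Mean estimates were -0.498 to -0.501 for a true -0.5. Type I error was 4.6% to 5.8%, close to the model with visit-specific slopes in the same runs.

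**The case against.** A reader might infer that the Week 16 PP difference is definitely adjusted with the wrong slope. The documents do not support that. They give no baseline SD and no baseline-to-visit slopes or correlations, and if the slopes are equal nothing is lost.

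A reader might also infer that the early visits dominate the shared slope. Section 8.9 gives a single conditional SD, for the Week 16 calculation. If 0.82 held at every visit, Week 16 would carry half the weight, about the same as Week 4. Dominance by Week 4 needs residual SDs that grow over time, which is an assumption. The larger losses rest on it.

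A third tempting step is that this restriction alone could trigger the FAS-PP investigation. Section 8.5.1 speaks of substantial differences in conclusions. A shift of a few hundredths of a percentage point or a slightly wider interval would rarely produce one, and the two analyses already differ in population and model. A baseline imbalance large enough to matter is also uncommon: 0.2 is about 1.8 standard errors (0.7 x sqrt(1/57 + 1/114) = 0.114).

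All of this stands and limits the size of the point. It does not remove the literal reading: the PP model names no baseline-by-time term, and no cLDA term supplies one.

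**Conclusion.** The point holds as a minor one about a secondary analysis. As written, the PP model restricts baseline adjustment in a way that the primary model does not.

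The cost is conditional on slopes that differ between visits. It is about 0.5% to 2% of Week 16 variance if the conditional SD is constant, and about 2.5% to 16% under the assumed growing SDs. Even at 16%, power for a 0.5% difference in 171 subjects stays near 94%.

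The shared slope causes no systematic bias under randomisation, although the PP set is itself selected after randomisation. The primary cLDA test and its stated 97% power are unaffected. The size for FPG was not calculated, because the plan gives no correlation matrix for it.

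**What to change.** In the Section 8.6.1 sentence on the PP model, name the covariates as *baseline value and the interaction of baseline value by time*. This should apply to both the HbA1c and the FPG PP analyses.

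It gives the PP model the same flexibility in baseline adjustment as the cLDA, so that FAS-PP differences reflect baseline handling less. The cost is a few words and 3 more degrees of freedom, with no new data. If the interaction is already intended, the sentence should say so.

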3.2 Secondary Objective(s) & Hypothesis(es)

[Phase A (double-blind period)]

1. **Objective:** To assess the efficacy of omarigliptin 25 mg q.w. compared to placebo based upon change from baseline in fasting plasma glucose (FPG) at Week 16.

Hypothesis: Omarigliptin 25 mg q.w. provides greater reduction in FPG compared with placebo as assessed by change from baseline to Week 16.

2. **Objective:** To assess the efficacy of omarigliptin 25 mg q.w. compared to placebo based upon proportion to goal of HbA1c <7.0% or <6.5% at Week 16.
3. **Objective:** To assess the efficacy of omarigliptin 25 mg q.w. compared to placebo based upon change from baseline in 1, 5-anhydroglucitol (1, 5-AG) at Week 16.

[Phase A (double-blind period) and Phase B (open-label period)]

4. **Objective:** To assess the efficacy of omarigliptin 25 mg q.w. for up to 52 weeks on glycemic control parameters (change from baseline in HbA1c and FPG, and proportion to goal of HbA1c <7.0% or <6.5%).

4.0 BACKGROUND & RATIONALE

4.1 Background

Refer to the approved labeling for information on omarigliptin (MK-3102).

4.1.1 Pharmaceutical and Therapeutic Background

Diabetes mellitus (DM) is a metabolic disorder characterized by chronic hyperglycemia due to insufficient insulin action [1] [2]. DM is classified into two types on the basis of its etiology: Type 1 DM (due to an autoimmune mechanism, idiopathic) and Type 2 DM (T2DM) (due to insulin resistance increased and an insulin secretory defect) [1] [2]. T2DM, which accounts for more than 95% of DM [2], is associated developing with environmental factors, aging and several genetic factors [1]. Chronic hyperglycemia contributes to the development of diabetic complications such as retinopathy, nephropathy, neuropathy and atherosclerosis, and significantly poor quality of life (QOL) of patients with DM [1].

It is estimated that 415 million people worldwide (8.8% of adults) have DM in 2015, and the number of people with the disease is predicted to rise to 642 million by 2040 (Approximately 55% increase compared to 2015) [3]. The number of adult people with DM is also rising in Japan. According to the National Health and Nutrition Examination Survey by the Ministry of Health, Labor and Welfare (MHLW), the number of people ≥ 20 years old in Japan who are strongly suspected of DM is increasing annually, counting approximately 7.4 million in 2002, 8.9 million in 2007, and 9.5 million in 2012 [4]. Of those, approximately more than 65% of the people are expected to take some kind of AHAs [4].

In Japan, the improvement of lifestyle by diet, exercise, and patient education is the foundation of treatment for T2DM. If the target value of glycemic control is not achieved with diet and exercise for 2 or 3 months, medication treatment is initiated according to clinical condition of individual patient [1]. For the selection of medication treatment, age, degree of obesity, intensity of chronic complication, renal and hepatic function, and capacity of insulin secretion and the intensity of insulin resistance, in addition to severity of metabolic disorder, should be considered, and an oral AHA such as sulfonylureas (SU), glinides, biguanides (BGs), thiazolidinediones (TZD), α -glucosidase inhibitors (α -GI), dipeptidyl peptidase 4 (DPP-4) inhibitors, and sodium glucose cotransporter 2 (SGLT2) inhibitors or injectable AHAs, such as insulin or glucagon-like peptide 1 (GLP-1) receptor agonists can be selected [1]. When glycemic control is inadequately maintained with monotherapy and modification of lifestyle, up-titration of the oral AHA, co-administration of oral AHAs with different mechanisms of action, switching to GLP-1 receptor agonists or insulin, or co-administration of oral AHAs with a GLP-1 receptor agonist or insulin can be considered [1].

In 2013, proportion of the T2DM patients who received insulin (insulin monotherapy or co-therapy of insulin and oral AHAs) is approximately 21.6% in Japan. This percentage is the second highest following the percentage of the patients (59.4%) who were treated with any oral AHAs only, indicating that insulin treatment is commonly used in Japan [5]. When glycemic control is inadequately treatment with insulin monotherapy, up-titration of insulin or insulin intensification therapy will be administered to improve hyperglycemia after eating. However, it is considered as barrier to adequate glycemic control since it may cause risks of increasing of hypoglycemia, or it may cause increasing burden of frequently injection of insulin. On the other hand, combination with insulin and oral AHAs (SUs, BGs, TZD, α -GI, DPP-4 inhibitors) will show improving of glycemic control or decreasing insulin totally dosage [2].

DPP-4 inhibitors such as omarigliptin improve glycemic control in subjects with T2DM by increasing insulin secretion, mediated by an enhancement of the "incretin" axis. Incretins,

which are gut-derived hormones that include GLP-1 and glucose-dependent insulinotropic peptide (GIP), are endogenous insulin secretagogues that act in a glucose-dependent manner to stimulate insulin secretion [6, 7, 8 and 9]. Following a meal, incretins are released from intestinal cells into the circulation. Both GLP-1 and GIP stimulate insulin release; in addition, GLP-1 suppresses glucagon release [9].

Therapies that target the incretin axis, including DPP-4 inhibitors such as omarigliptin, have several potential advantages over conventional insulin secretagogues such as SUs. First, as noted above, incretin stimulation of insulin release is glucose-dependent. For this reason, the risk of hypoglycemia when DPP-4 inhibitors are administered as monotherapy or in combination with agents not known to cause hypoglycemia is low. Second, DPP-4 inhibitors have generally neutral effects on body weight, whereas SUs are associated with an increase in body weight [10].

Omarigliptin is unlike the presently marketed DPP-4 inhibitors that are administered once or twice daily, omarigliptin has a half-life ($t_{1/2}$) that supports once-weekly dosing. The efficacy, safety, and tolerability of omarigliptin 25 mg once weekly was evaluated in two Japanese studies (in monotherapy and as add-on therapy to 5 classes of AHA) in patients with T2DM. In the double-blind period of Japan phase III placebo- and sitagliptin-controlled monotherapy study (P020) omarigliptin 25 mg once-weekly demonstrated superiority to placebo and non-inferiority to sitagliptin 50 mg once-daily in change from baseline in HbA1c at Week 24. When administered omarigliptin 25 mg once-weekly for up to 52 weeks, omarigliptin achieved a sustained effect with generally safe and well tolerated profile. In the double-blind period of Japan phase III add-on to oral AHA study (P015), omarigliptin 25 mg once weekly was added-on to other classes of oral AHA monotherapy with different mechanisms of action likely to be used clinically in Japan including SUs, glinides, BGs, TZD, or α -GI. As combination with all of the aforementioned AHA classes, the change from baseline in HbA1c at Week 24 with the addition of omarigliptin 25 mg was superior to the addition of placebo. When administered omarigliptin 25 mg once-weekly for up to 52 weeks, omarigliptin achieved a sustained effect with generally safe and well tolerated profile.

Based on above results, omarigliptin was launched in the market in Japan in November 26 2015, for the treatment of T2DM.

As indicated above, the addition of omarigliptin to the subjects with T2DM who received insulin therapy will be anticipated to show good efficacy and safety profile.

